| 5.1 ADDITIONAL STUDY SITES | 9 |
| 6. STUDY POPULATION | 9 |
| 7. IDENTIFICATION AND ENROLLMENT OF SUBJECTS | 10 |
| 7.1 RECRUITMENT AND PRE-SCREENING | 10 |
| 7.2 PAYMENT TO SUBJECTS | 11 |
| 7.3 INFORMED CONSENT | 11 |
| 7.4 WITHDRAWAL CRITERIA..... | 11 |
| 8. PROCEDURES INVOLVED | 12 |
| 10. DATA MANAGEMENT | 17 |
| 11. DATA AND SPECIMEN BANKING | 17 |
| 14. RISKS TO SUBJECTS | 19 |
| 15. POTENTIAL BENEFITS TO SUBJECTS..... | 19 |
| 17. ETHICAL CONSIDERATIONS | 20 |
| 18. PUBLICATIONS | 20 |
| 19. REFERENCES..... | 20 |

List of Abbreviations and Definition of Terms

| | |
|---------|--|
| AE | Adverse Events |
| BPH | Benign Prostatic Hyperplasia |
| BRB | Biomedical Research Building |
| CNS | Central Nervous System |
| CRF | Case Report Form |
| CTCAE | Common Terminology Criteria for Adverse Events |
| eCRF | Electronic Case Report Form |
| ED | Erectile Dysfunction |
| EDITS | Erectile Dysfunction Inventory of Treatment Satisfaction |
| EDV | End Diastolic Velocity |
| GCP | Good Clinical Practice |
| HIPAA | Health Information Portability and Accountability Act |
| ICF | Informed Consent Form |
| ICH | International Conference of Harmonization |
| ICI | Intracavernosal Injection |
| IEC | Institutional Ethics Committee |
| IIEF | International Index of Erectile Function |
| IIEF-EF | Erectile Function Subdomain Score |
| IRB | Institutional Review Board |
| ISCI | Interdisciplinary Stem Cell Institute |
| MCID | Minimal Clinically Important Difference |
| mL | Milliliter |
| ng/dL | Nanograms Per Deciliter |
| PDE5i | Phosphodiesterase 5 inhibitor |
| PPP | Platelet Poor Plasma |
| PRFM | Platelet Rich Fibrin Matrix |
| PRP | Platelet Rich Plasma |
| PSV | Peak Systolic Velocity |
| RCT | Randomized Controlled Trial |
| SAE | Serious Adverse Events |
| SEP3 | Sexual Encounter Profile |
| SOP | Standard Operating Procedure |
| SSRI | Selective Serotonin Reuptake Inhibitor |
| TE-SAE | Treatment Emergent Serious Adverse Events |
| UM | University of Miami |
| VAS | Visual Analogue Pain Scale |

| Protocol Synopsis | |
|--------------------------------|---|
| TITLE | A Randomized, Double-Blind, Placebo Controlled Trial on Safety and Efficacy of Autologous Platelet-Rich Plasma for Treatment of Erectile Dysfunction |
| SPONSOR | University of Miami, Miller School of Medicine, Department of Urology |
| PHASE OF STUDY | Phase I |
| STUDY THERAPY | Autologous Platelet-Rich Plasma (PRP) |
| STUDY DESIGN | Randomized, Double Blind, Placebo Controlled, Pilot Trial |
| ROUTE OF ADMINISTRATION | Intracavernosal Injection |
| SUBJECT POPULATION | 80 male subjects between the age of 30-75 with erectile dysfunction of organic origin |
| STUDY OBJECTIVES | 
Primary: To investigate and compare the treatment efficacy of PRP vs placebo treatment in men with mild-moderate ED, as measured by IIEF.
 
Secondary: To study incidence of adverse events and safety of PRP injection treatment in men with mild-moderate ED, as measured by IIEF.
 |
| INVESTIGATION PLAN | 
80 men with Erectile Dysfunction (ED) of organic origin, that meet all of the inclusion and none of the exclusion criteria, will be randomized to receive, intracavernosal injection of either PRP or placebo in a 1:1 double-blinded fashion:
 
Group A (40 subjects): Autologous PRP All subjects in this group will receive 2 sessions of autologous PRP with 30 ± 7 day treatment interval. 5mL of PRP will be injected at each session.
 
Group B (40 subjects): Placebo (Normal Saline) All subjects in this group will receive 2 sessions of normal saline with 30 ± 7 day treatment interval. 5mL of normal saline will be injected at each session.
 
 - Patients will be followed for outcome assessments at 1, 3, and 6 months post final injection. |
| DURATION OF STUDY | 9 months (1 month screening, 2 therapy sessions 1 month apart, 6 months follow-up) |
| DEFINITION OF ENDPOINTS | 
Primary Endpoint (Efficacy)
 
 - The percentage of subjects in each group who attain MCID in IIEF-EF domain from baseline to 4 weeks after final treatment. 
Secondary Endpoints (Efficacy)
 
 - The percentage of subjects in each group who attain MCID in IIEF-EF domain from baseline to 12 & 24 weeks after final treatment. - The difference between groups in change of IIEF-EF score from baseline to 4, 12, & 24 weeks after final treatment. - Differences in Doppler ultrasound parameters (PSV and EDV) from baseline to 24 weeks after final treatment. 
Secondary Endpoints (Safety)
 
 - Incidence of adverse events in all patients during the study period. |

| | |
|--------------------|--|
| INCLUSION CRITERIA | 
 1. Be Male 2. Be 30 to ≤75 years of age (inclusive). 3. Be able to provide written informed consent. 4. Have a diagnosis of ED due to organic origin for at least 6 months prior to consent. 5. Sexually active in a stable, heterosexual relationship of more than three months duration. 6. IIEF-EF score 11-25 at screening (even if taking a single PDE5i). 7. Agree to attempt sexual intercourse at least 4 times per month for the duration of the study without being under the influence of alcohol or recreational drugs. 8. Agree to comply with all study related tests/procedures. |
| EXCLUSION CRITERIA | 
 1. Previous penile surgery of any kind (except circumcision and condyloma removal), such as penile lengthening, penile cancer surgery, penile plication, grafting. 2. Previous history of priapism or penile fracture 3. Abnormal morning serum testosterone level defined as a value lower than 300 ng/dL ($\pm 5\%$) (indicative of untreated hypogonadism), or greater than 1197 ng/dL ($\pm 5\%$). 4. Current or previous hormone usage, other than prescribed testosterone, clomiphene or thyroid medication. (Subjects with prior or current use of hormonal treatment for prostate cancer are also excluded.) 5. Psychogenic ED as determined by study investigator. 6. Anatomical (Peyronie's Disease or penile curvature that negatively influences sexual activity) or neurological abnormalities in the treatment area. 7. Patients using ICI for management of ED 8. Patients with generalized polyneuropathy, or neurological conditions irrespective of cause, such as severe diabetes, multiple sclerosis or Parkinson's disease. 9. Have a serious comorbid illness/condition/behavior that, in the opinion of the investigator, may compromise the safety or compliance of the subject or preclude successful completion of the study. 10. History of consistent treatment failure with PDE5 inhibitors for therapy of ED. 11. Any history of significant psychiatric disease, such as bipolar disorder or psychosis, greater than one lifetime episode of major depression, current depression of moderate or greater severity. Patients who are currently using SSRI or psychotropic medications. 12. Hemoglobin a1c >9%. |

1. Protocol Title

A Randomized, Double-Blind, Placebo Controlled Trial on Safety and Efficacy of Autologous Platelet-Rich Plasma for Treatment of Erectile Function

2. Background

2.1 Platelet-based therapies

Platelet-derived therapies are a growing trend across multiple medical and surgical specialties including dermatology, ophthalmology, cardiology, colorectal surgery, plastic surgery and mainly orthopedics [1-2]. One of the most well described platelet-based therapies is autologous platelet-rich plasma (PRP) [3]. PRP is derived from the centrifugation of whole blood with a separator gel to remove the red and white blood cells. The resulting supernatant has a greater than four-fold increase in platelets and other plasma proteins [1]. This concentrate is then administered via injection. PRP has been frequently used for orthopedic conditions such as bone and soft tissue trauma, inflammatory conditions, and chronic pain syndromes [3-4]. Evidence suggests that platelets play an important role not only in coagulation but also in regulation of body metabolism, promotion of the wound healing, tissue regeneration, vascular remodeling and inflammatory/immune responses through secretion of growth factors, cytokines and chemokines [4-5]. These biologically active proteins include transforming growth factor- β , platelet-derived growth factor, platelet-derived epithelial growth factor, insulin-like growth factor, vascular endothelial growth factor, basic fibroblast growth factor, as well as many others [6]. When platelets are activated, they release these growth differentiation factors, facilitating even nerve repair and regeneration [7-8]. Growth factors act locally and are implicated in many aspects of natural wound healing, including chemotaxis, cell proliferation, cell differentiation and angiogenesis. They also control and conduct synthesis, modification and degeneration of extracellular matrix proteins. Coordination of these cellular and molecular processes is integral to proper wound healing and tissue regeneration [9]. The key role of platelets in these processes makes them an attractive candidate for therapies aimed at accelerating natural healing, as well as tissue regeneration.

Autologous blood-based biomaterials are promising therapeutic options for varied pathology. Rapid generation of therapeutic material following collection allows for point-of-care therapy [10]. Furthermore, an autologous therapy avoids the need for immunosuppression and eliminates concerns of rejection. Newer strategies to prolong the anti-inflammatory and wound healing properties of platelets have focused on creating a fibrin matrix (platelet rich fibrin matrix, PRFM) to bind the platelets and prevent extravasation from the site of injection, thereby addressing the concern of early washout with PRP [11]. In addition, PRFM offers a potential scaffold for tissue ingrowth and may allow continued release of platelet-related factors for a longer duration. Across multiple disciplines, PRP has been used both as a primary treatment modality and as a supplement to other therapies in hopes of supplementing wound healing, tissue regeneration, and angiogenesis. Although most of the studies focusing on PRP injections have been relatively small and heterogeneous, they largely support the concept of administration in terms of safety, while efficacy remains uncertain. Finally, the concept of

autologous therapy has been shown in the real world that it is particularly attractive to patients [10].

2.2 Platelet-rich plasma treatment for erectile dysfunction

Erectile dysfunction (ED) affects as many as 1 in 4 men, and evidence indicates that incidence is rising [12-13]. The pathophysiology is multifactorial, but the most common pathophysiology, vasculogenic erectile dysfunction, has as first sign endothelial dysfunction secondary to inflammation [14]. The most common treatments for ED aim to improve endothelial function through augmentation of the nitric oxide pathway [15]. Return of potency after surgical injury of CNS partially depends on axon regeneration in the remaining neural tissue [16]. The process of regeneration and functional recovery of peripheral nerve is slow and is influenced by many factors [17] such as extracellular matrix, neurotrophic factors, and cellular components [18]. Recent advances in the understanding of molecular pathways and their physiological role demonstrate that growth factors are an important part of the development, maintenance, and regeneration of the nervous system [19]. Various growth factor neuromodulatory strategies, including insulin-like growth factor (IGF-I) and neurotrophic factors, are investigated to identify agents that may have neuroprotective and regenerative function after the occurrence of peripheral nerve injury. Accumulating evidence indicates that neuroimmunophilin ligand (such as FK506) plays a significant role in neural regeneration and upregulation of neuronal nitric oxide synthase (nNOS), as well as in the recovery of erectile function after CN injury occurrence [20-21]. FK506 neuroprotection after CN injury is mediated by antioxidative/nitrosative and anti-apoptotic pathway [22]. When platelets are activated, they release many kinds of growth differentiation factors and a few types have been found to facilitate nerve repair and regeneration. Moreover, corporeal dysfunction due to smooth muscle atrophy or other intracavernosal pathology can lead to corporo-venous occlusive erectile dysfunction despite a normal arterial inflow. Rejuvenating the Corporeal tissues with PRP, which is well known for its growth and healing factors, is a possible modality as a potential treatment for erectile dysfunction according to Alkhayal et al [23]. In their retrospective study examining the efficacy of one intra-cavernosal PRP injection to 40 ED patients, they reported that mean IIEF-5 score before treatment was 13 (5-20) and post treatment IIEF-5 = 17 (7-24), ($p < 0.001$). Other studies have shown similar results with minimal side effects, no serious adverse reactions and potential efficacy (Table 1) [23-26].

| Human Studies of PRP for ED | | | | | | | |
|-----------------------------|------|--------------------|---|---|----------|---|---|
| Author | Year | Number of Patients | Patient Population | Administration | Followup | Adverse Events | Conclusion |
| Banno [26] | 2017 | N=9 | Penile Rehab | PRP ICI into Penises with Vacuum Device | 4 weeks | No AEs reported | PRP may represent a safe and viable option as a supplementary therapy for penile rehabilitation. Particularly notable is the prospect of zero side effects. |
| Matz [24] | 2018 | N=16 | Erectile dysfunction, Peyronies Disease | PRP with CaCl ICI | 15.5m | Minor: Bruising 1, Mild Pain 4. Major: none | PRFM injections for ED, PD, and female SUI are feasible and safe. Although the limited data is suggestive of efficacy, a placebo control will be required in subsequent efforts for confirmation |
| Epifanova [25] | 2019 | N=10 | Erectile Dysfunction | 6 injections PRP with CaCl2 and Shockwave | 60 Days | No AEs reported | There were no serious adverse events as well as severe adverse events. Erectile dysfunction symptoms in all men participated in the study significantly decreased after treatment with PRP-therapy and extracorporeal shockwave therapy |
| Alkhayal [23] | 2018 | N=40 | Erectile Dysfunction | 1 injection PRP | >1 month | No AEs reported | Platelet rich plasma is a safe and efficacious option for penile rejuvenation and improvement of erectile dysfunction |

Table 1: Summary of published studies and abstracts

To date, there are no treatments that address the underlying cause of endothelial dysfunction, although LIST treatment for ED has shown promising results. Platelet-derived therapies targeting inflammation and promoting tissue/nerve regeneration and may represent a potential treatment option towards this direction. Despite growing evidence to the efficacy of PRP, no randomized placebo-controlled studies exist.

3. Study Objectives

3.1 Primary Objective:

To investigate and compare the treatment efficacy of PRP vs placebo treatment in men with mild-moderate ED, as measured by IIEF.

3.2 Secondary Objective:

To study the adverse events and safety of the PRP treatment in men with mild-moderate ED, as measured by IIEF.

4. Study Endpoints

4.1 Primary Endpoint:

- The percentage of subjects in each group who attain MCID in IIEF-EF domain from baseline to 4 weeks after final treatment.

4.2 Secondary Endpoints (efficacy):

- The percentage of subjects in each group who attain MCID in IIEF-EF domain from baseline to 12 & 24 weeks after final treatment.
- The difference between groups in change of IIEF-EF score from baseline to 4, 12, & 24 weeks after final treatment.

- Differences in Doppler ultrasound parameters (PSV and EDV) from baseline to 24 weeks after final treatment.

4.3 Secondary Endpoints (safety):

- Incidence of adverse events in all patients during the study period. Anticipated adverse events that will be recorded at every visit are the following
 - o Pain
 - o Bruising
 - o Swelling
 - o Edema
 - o Allergy
 - o Penile Fracture
 - o New Penile Curvature

4.4 Exploratory Endpoints:

- Change in stretched penile length from baseline to 24 weeks after final treatment.
- The percentage of subjects in each group who attain MCID in IIEF-EF domain from baseline to 4 weeks after final treatment.

5. Study Location

The study will be funded by the Department of Urology and coordinated by the University of Miami (UM), Miller School of Medicine, Department of Urology. The UM Interdisciplinary Stem Cell Institute (ISCI) will also support the project (logistics, quality control, management, storage of specimens and data). All study visits will be carried out in the Department of Urology clinics, (ADDRESS: [name], University of Miami Miller School of medicine, Miami, FL. & Lennar address) PRP preparation will take place in the clinic's andrology lab.

5.1 Additional Study Sites

No additional study sites.

6. Study Population

80 males with ED of organic origin. All patients will be regular PDE5i users/responders. After a 1-month wash-out period for PDE5i, men with ED will be evaluated by IIEF-EF domain and eligible patients will be randomized to one of 2 treatment groups with an equal allocation ratio (1:1). Participants who do not adhere to the 1-month wash-out period, or do not meet the IIEF-EF domain score will be considered a screen failure and will not receive the study therapy.

6.1 Inclusion criteria: In order to participate in this study, a patient must:

- 1) Be Male
- 2) Be 30 to 75 years of age (inclusive).

- 3) Be able to provide written informed consent.
- 4) Have a diagnosis of ED due to organic origin for at least 6 months prior to consent.
- 5) Sexually active in a stable, heterosexual relationship of more than three months duration.
- 6) IIEF-EF score 11-25 at screening (even if taking a single PDE5).
- 7) Agree to attempt sexual intercourse at least 4 times per month for the duration of the study without being under the influence of alcohol or recreational drugs.
- 8) Agree to comply with all study related tests/procedures.

6.2 Exclusion criteria: In order to participate in this study, a patient must not:

- 1) Previous penile surgery of any kind (except circumcision and condyloma removal), such as penile lengthening, penile cancer surgery, penile plication, grafting.
- 2) Previous history of priapism or penile fracture
- 3) Abnormal morning serum testosterone level defined as a value lower than 300 ng/dL ($\pm 5\%$) (indicative of untreated hypogonadism), or greater than 1197 ng/dL ($\pm 5\%$).
- 4) Current or previous hormone usage, other than prescribed testosterone, clomiphene or thyroid medication. (Subjects with prior or current use of hormonal treatment for prostate cancer are also excluded.
- 5) Psychogenic ED as determined by study investigator.
- 6) Anatomical (Peyronie's Disease or penile curvature that negatively influences sexual activity) or neurological abnormalities in the treatment area.
- 7) Patients using ICI for management of ED
- 8) Patients with generalized polyneuropathy, or neurological conditions irrespective of cause, such as severe diabetes, multiple sclerosis or Parkinson's disease.
- 9) Have a serious comorbid illness/condition/behavior that, in the opinion of the investigator, may compromise the safety or compliance of the subject or preclude successful completion of the study.
- 10) History of consistent treatment failure with PDE5 inhibitors for therapy of ED.
- 11) Any history of significant psychiatric disease, such as bipolar disorder or psychosis, greater than one lifetime episode of major depression, current depression of moderate or greater severity. Patients who are currently using SSRI or psychotropic medications.
- 12) Hemoglobin a1c >9%.

7. Identification and Enrollment of Subjects

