7.1 Recruitment and Pre-screening

The research coordination team may develop materials to aide in recruitment. This may include, but is not limited to, informational videos and brochures which provide education about erectile dysfunction and include information about the study; physician referral letter templates which can be used to promote awareness of the study in the urology community; flyers/posters which can be utilized at approved clinic locations and as part of health fair materials; templates for print advertisements which can be utilized in

newsprint and media campaigns. Not all materials have been developed prior to trial initiation, however each of these recruitment methods will be reviewed and approved by the IRB prior to use.

Pre-screening of subjects includes reviewing medical records and imaging studies for inclusion/exclusions prior to consent. From the review of subjects' medical records and imaging studies on file, subjects who are determined to have a diagnosis of erectile dysfunction of organic origin, and have mild-moderate erectile function as assessed by IIEF-EF, as stated in Section 6.1, and also do not have evidence in their medical record of study exclusions stated in Section 6.2, are eligible to be consented to the study.

Investigators will inform research staff of potential participants who have been identified through pre-screening so the subjects can be approached to discuss the study and conduct the informed consent session. No study procedures will take place prior to the subjects signing of the informed consent form.

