8.1 Schedule of Events

The time and events table for the conduct of this study is shown below:

Table 1:

| Study Phase | Screening | | Injection | | Follow Up | | |
|---------------------------------|-----------------------------|-----------|------------------|-----------------------------|------------------------------|-------------------------------|---|
| | V1 | V2 | V3 | V4 | V5 | V6 | |
| Time Point | V1 | V2 | V3 | V4 | V5 | V6 | |
| Visit Window | 0 - 28days prior to therapy | Day 0 | Day 28 ± 7 | Week 4 Day 30 ± 7 | Week 12 Day 90 ± 7 | Week 24 Day 180 ± 7 | |
| Informed Consent | X | | | | | | |
| Demographics | X | | | | | | |
| Medical History | X | | | | | | |
| Physical Exam | X | | | | | | |
| Doppler Ultrasound | X | | | | | | X |
| Concomitant Medications/Therapy | X | X | X | X | X | | X |
| Review Adverse Events | | X | X | X | X | | X |
| Randomization | | X | | | | | |
| Study Therapy Injection | | X | X | | | | |
| Questionnaires | IIEF | X | | X | X | | X |
| | SEP3 | X | | X | X | | X |
| | EDITS | | | X | X | | X |
| | VAS | | X | X | | | |
| Laboratory Testing | Hematology | X | | | | | |
| | Chemistry | X | | | | | |
| | HbA1c | X | | | | | |
| | Testosterone | X | | | | | |

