8.3 Description of Study Visits

8.3.1 Visit 1: Screening Visit

Visit 1 (0 – 28 days before therapy): The basic work-up will take place, including medical and sexual history, as well as necessary lab tests (testosterone, prolactin, hematology, chemistry), if not available during the last 12 months prior to screening. Subjects will complete the IIEF-ED questionnaire. We will ensure that patients have 4 attempts for intercourse, which they will record on the SEP diaries. PDE5i use is prohibited throughout the study. Screening visit can occur on same day as first injection. Refer to table 1 for procedures to be performed at the Screening visit.

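### The 1-month PDE5i wash-out in Section 6 is not reconciled with a screening window of at most 28 days that also permits same-day injection, which leaves eligibility and the baseline IIEF-EF open to interpretation

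*Combined protocol and SAP*

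**What the plan says.** Section 6 states of the population: "All patients will be regular PDE5i users/responders". It then sets the order of events: "After a 1-month wash-out period for PDE5i, men with ED will be evaluated by IIEF-EF domain and eligible patients will be randomized". The consequence of missing the wash-out is explicit: "Participants who do not adhere to the 1-month wash-out period, or do not meet the IIEF-EF domain score will be considered a screen failure". Such men do not receive study therapy.

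Criterion 6 in Section 6.1 sets the entry score as "IIEF-EF score 11-25 at screening (even if taking a single PDE5" (the synopsis has the same rule), so a man may be on drug when that score is taken.

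The schedule in Section 8.1 takes consent at Visit 1 and gives that visit's window as "0 - 28days prior to therapy". Section 8.3.1 adds: "Screening visit can occur on same day as first injection". The same section says "PDE5i use is prohibited throughout the study" and expects four intercourse attempts recorded in SEP diaries.

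Section 8.2.10 accepts an IIEF up to 6 months old, with no condition about PDE5i use. Section 8.3.2 has the IIEF completed and the diaries evaluated at the injection visits, with randomisation on Day 0 once eligibility is confirmed. Section 7.1 says "No study procedures will take place prior to the subjects signing of the informed consent form". The schedule has no wash-out start date, visit or check.

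**The concern.** The wash-out is a pass/fail entry condition that, by Section 6, applies to every man. The visit schedule does not appear to have been built around it. If the man's last dose is at or after Visit 1, the time available before Day 0 is at most the length of the screening window, and the same-day sentence reduces it to zero. A coordinator working from Section 6 and one working from Sections 8.1 and 8.3.1 could reach opposite decisions about the same man.

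The primary endpoint is also at stake. It is the proportion of men whose IIEF-EF rises by the MCID from baseline to 4 weeks after the last injection. Follow-up is off PDE5i. If the baseline was taken on drug, or before the drug effect was fully withdrawn, the change score mixes withdrawal of an effective drug with whatever the injection does.

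**Working it through.** **Inputs.** Wash-out: 1 month, before the IIEF-EF evaluation (Section 6). Gap from Visit 1 to Day 0: g = 0, 1, ..., 28 days (Section 8.1), with g = 0 expressly allowed (Section 8.3.1). Length of a month: not defined, so m is taken as 28, 30, 30.44 (average calendar month) or 31 days. Working assumption: the man is still on a PDE5i at Visit 1, as criterion 6 permits, and stops that day.

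**Step 1. Does the wash-out fit?** It is complete by Day 0 if g ≥ m. The shortfall is m − g when positive.

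| m (days) | Values of g that fit | Shortfall at g = 28 | Shortfall at g = 0 |
|---|---|---|---|
| 28 | 28 only | 0 | 28 |
| 30 | none | 2 | 30 |
| 30.44 | none | 2.44 | 30.44 |
| 31 | none | 3 | 31 |

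With m = 28, gaps of 0 to 27 days fall 28 to 1 days short, so Day -28 works with no slack.

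**Step 2. Which month do the documents use?** Both. The synopsis calls screening one month, and Section 8.1 gives it as 0 to 28 days. The injection interval is 30 ± 7 days in the synopsis and Section 8, but 28 ± 7 days in Sections 8.1 and 8.3.2. Follow-up is labelled Weeks 4, 12 and 24 (28, 84 and 168 days) in the same cells as Days 30, 90 and 180. The text therefore does not settle m.

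**Step 3. Diaries.** With g = 0 there is no time after Visit 1 in which to record the four attempts that Section 8.3.1 expects and Section 8.3.2 evaluates at the injection visit.

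**Step 4. Effect on the endpoint.** Let Δ be a man's true change from his off-drug level, and d the IIEF-EF points he still owes to a PDE5i at baseline. The recorded change is Δ − d, so he meets the MCID only if Δ ≥ MCID + d. Section 13.2 gives an MCID of 2 for mild and 5 for moderate ED. If his severity class is unchanged, the bar rises by d. If the drug moves him from moderate to mild, the bar becomes 2 + d instead of 5, which is higher only when d exceeds 5 − 2 = 3. The documents give no value for d, so neither the size nor the overall direction of the effect on response rates can be stated.

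**The case against.** The best defence is that the sections can all be obeyed. The window and the same-day sentence are permissions, while Section 6 is mandatory. If a month is read as 28 days, which the synopsis supports, a coordinator can place Visit 1 on Day -28, have the man stop then, and take the IIEF and the eligibility decision at Visit 2 before randomising. A man already off PDE5i before Visit 1 would also comply, and no text says the wash-out starts at consent. The synopsis duration offers a further opening: its parts sum to 1 + 1 + 6 = 8 months against a stated 9, so one might suppose a separate wash-out month.

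Much of this stands, and it rules out several stronger readings:

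- A reader might infer that the wash-out cannot fit at all. Day -28 with a 28-day month shows otherwise.
- A reader might infer that men will be injected after short wash-outs. Section 6 prescribes screen failure, so such an injection would be a deviation that the same-day sentence invites, not the plan's rule.
- A reader might turn the single workable gap out of 29 into a share of men lost. Those are calendar gaps, not patients, and nothing in the documents says how visits will be distributed over them.

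The defence does not remove the conflict. Criterion 6 expressly admits men on drug at screening, and for them same-day injection and the wash-out rule are incompatible under any definition of a month. A stop before consent made only to qualify would sit badly with Section 7.1, and the protocol does not address it. The unexplained ninth month is not assigned to wash-out or to anything else.

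**Conclusion.** The point holds as an inconsistency with consequences, not as an impossibility. For a man still on a PDE5i at Visit 1, the wash-out fits on one permitted day at most, on none if a month is 30 or 31 days, and never with same-day screening. This rests on his stopping at Visit 1, which the protocol neither states nor excludes.

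Two consequences follow. Eligibility can depend on which section is applied. And the baseline IIEF-EF may be on drug, partly washed out, or up to 6 months old, and so not comparable with off-drug follow-up. Section 8.3.2 makes a post-wash-out Day 0 score possible, but nothing names it as the baseline.

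A reader might go further and infer a bias toward PRP. The documents do not support that: randomisation follows eligibility, so on-drug or partly washed-out baselines should be balanced between arms in expectation. The harm is to the definition of the population and to the response rates, in both arms. It should be corrected, and it does not by itself invalidate the comparison.

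**What to change.** Reconcile Sections 6, 6.1 (criterion 6, and its copy in the synopsis), 8.1, 8.2.10, 8.3.1 and 8.3.2 so that five items agree: the number of days in the wash-out month; when the wash-out starts relative to consent; the Visit 1 window; the same-day screening sentence, including its fit with the SEP diary requirement; and which IIEF-EF decides eligibility and serves as baseline. For the last item, the baseline should be the score obtained under the wash-out condition that Section 6 already states, named as such in the endpoint definition. No position is taken here on how long the wash-out should be or which clinical rule is right.

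The cost is a short amendment. Depending on how the sponsor reconciles the text, men who would have been screened and injected on one day may need a longer screening period and a separate visit.
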